4.1 Within-Group Longitudinal Analyses

For evaluating changes over time within each experimental arm, distinct approaches will

be employed based on variable characteristics. Continuous variables meeting normality assumptions will be analyzed using repeated measures ANOVA with Greenhouse-Geisser correction for sphericity violations, followed by paired t-tests with Bonferroni-adjusted α levels for post-hoc timepoint comparisons when omnibus tests reach significance. Non-normal continuous data and all ordinal outcomes will utilize the Friedman test (non-parametric equivalent to repeated measures ANOVA) followed by Wilcoxon signed-rank tests for post-hoc comparisons with appropriate multiplicity adjustments. Effect sizes will be reported as Cohen's d for parametric analyses and rank-biserial correlations for non-parametric tests to quantify the magnitude of observed changes independent of sample size considerations.

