Low-load blood flow restriction (LL-BFR) training has emerged as an innovative rehabilitation strategy that combines low-intensity resistance exercise with partial vascular occlusion to enhance muscle growth and strength while using much lower loads than traditional resistance training (Hughes et al., 2017). Evidence suggests that BFR can safely stimulate muscle hypertrophy comparable to high-load training and may reduce joint stress, making it particularly suitable for patients recovering from ACLR (Scott et al., 2015). This pilot study aims to compare the effectiveness of LL-BFR and traditional resistance training in improving muscle size, strength, range of motion, pain, and joint effusion in patients following ACLR, contributing to the evidence base for optimal post-surgical rehabilitation strategies.

Objective

The main objective/s of the study is to compare the effectiveness of low load blood flow restriction training (LL-BFR) with traditional resistance training exercises (T-RT) at improving skeletal muscle hypertrophy, strength, Range of motion (ROM), pain and effusion in individuals who have undergone anterior cruciate ligament (ACL) reconstruction surgery.

Study Design

1. Study Type

Interventional: The study (Pilot randomized controlled trial) involves an active intervention (BFR-RT vs. T-RT) to evaluate treatment efficacy.

2. Primary Purpose

Treatment: The study aims to assess the therapeutic effectiveness of BFR-RT compared to traditional low load training in improving post-ACLR outcomes.

3. Study Phase

N/A: The trial does not involve investigational drugs or biologics.

4. Intervention Model

Parallel Design: Two distinct groups receive different interventions simultaneously:

Group 1 (BFR-RT): Low-load resistance training with blood flow restriction along with standard rehabilitation.

Group 2 (T-RT): Low-load traditional resistance training with standard rehabilitation.

- **Model Description:**

BFR-RT group undergoes 8 weeks of BFR training followed by standard rehabilitation protocol progression.

T-RT group receives standard rehabilitation alone for the entire duration.

5. Number of Arms

2 Arms:

Experimental Arm: BFR-RT.

Active Comparator Arm: T-RT.

6. Masking (Blinding)

- **Single-Assessor Blinded:**

Investigator: The researcher assessing outcomes is blinded to group assignments.

Participant: Participants are aware of their group (open-label for participants).

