Care Provider: Therapists administering interventions are unblinded.

None (Open Label): Not applicable; partial blinding is used.

6. Allocation

Participants are randomly assigned to BFR-RT or T-RT groups.

Method: Opaque envelopes with coded assignments prepared by an independent team member.

Stratification: Not specified, but typically balanced for age, sex, or baseline function.

7. Enrollment

- Target Sample Size: 32 participants.

Type: Actual (confirmed enrolled participants).

Justification: Based on power analysis to detect clinically significant differences in muscle hypertrophy/strength.

8. Additional Protocol Details

Intervention Protocol

Frequency: Biweekly sessions (16 total over 8 weeks).

BFR Technique:

- Occlusion band placed proximally on the affected limb.
- Tightness standardized to allow one finger beneath the band.

Standard Rehabilitation:

- Includes range of motion (ROM) exercises, strengthening, and functional training per hospital protocol.

Outcome Assessments

Time Points: Baseline (Week 0-1), Mid-Intervention (Week 4-5), Post-Intervention (Week 9).

Measures:

Primary: Muscle hypertrophy (ultrasound/MRI), strength (manual muscle testing).

Secondary: Pain (KOOS), knee ROM, effusion (circumference), adherence rates.

Safety Monitoring

- Adverse Events: Documented throughout; none reported in this trial.
- Exclusion Safeguards: No vascular pathologies or anticoagulant use.

9. Ethical Considerations

Informed Consent: Obtained from all participants.

Approval: Ethical approval was taken from the Institutional Review Board (IRB) of Rehman Medical Institute.

10. Participants:

- **Inclusion criteria:** Individuals who have undergone ACL reconstruction surgery within the past 4 weeks, free of any neurological impairments or significant cardiac, pulmonary, or metabolic conditions.
- **Exclusion criteria:** Individuals with contraindications to exercise, any other comorbidity, or systemic inflammatory conditions.

Outcome Measures:

- **Primary Outcome:** Muscle strength (measured using manual muscle technique). Muscle size (measured via measuring tape), ROM (Using goniometer), pain (using a Visual Analog Scale), and joint effusion (assessed clinically).

Statistical Analysis Plan

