This Statistical analysis plan (SAP) compares postoperative rehabilitation outcomes between an experimental training group (n=16) and a control group (n=16) across three key timepoints: immediate post-surgical baseline (0-1 week), mid-intervention (4-5 weeks), and post-intervention (8-9 weeks). The study employs a repeated measures design to evaluate five primary outcome domains: muscle size (continuous, cm), range of motion (continuous, degrees), muscle strength (ordinal, 0-5 scale), pain perception (ordinal, VAS 0-10), and joint effusion (ordinal, 0-3 clinical scale).

In contrast, This SAP includes descriptive statistics, normality assessments, inferential statistical tests with corresponding assumptions, multiple comparison adjustments, missing data handling procedures, and software implementation to ensure reproducibility.

1. Descriptive Statistical Approaches

Comprehensive descriptive analyses will precede all inferential testing to characterize the dataset and inform appropriate test selection. For continuous variables (muscle size, ROM), we will report means with standard deviations (SD) for normally distributed data and medians with interquartile ranges (IQR) and full ranges for non-normal distributions, supplemented by graphical representations including boxplots with superimposed individual data points to visualize both group trends and individual trajectories. Ordinal variables (strength, pain, effusion) will be summarized using median scores with IQRs and frequency distribution tables showing counts/proportions at each ordinal level, with stacked bar charts employed to visualize proportional changes across timepoints. These descriptive analyses will be stratified by group (experimental vs control) and timepoint to enable preliminary assessment of intervention effects and data distributions prior to formal hypothesis testing.

2. Data Characteristics and Variable Classification

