The dataset comprises both continuous and ordinal variables requiring distinct analytical approaches. Continuous variables including muscle circumference (measured via standardized tape measure protocol) and active range of motion (measured via goniometry by blinded assessors) will be analyzed for both central tendency and variability. Ordinal variables including manual muscle testing scores (Medical Research Council 0-5 scale), visual analog pain scores (recorded as integers 0-10), and clinician-rated effusion scales (0=none, 3=severe) will be analyzed using non-parametric methods due to their inherent rank-based properties and expected non-normal distributions. All variables will be assessed at three protocol-specified timepoints with identical measurement protocols maintained across groups to ensure comparability.

3. Normality and Parametric Assumption Testing

Formal statistical testing for normality assumptions will be conducted for all continuous variables prior to selecting inferential methods. The Shapiro-Wilk test ($\alpha=0.05$) will be applied to residuals from all continuous outcome measures within each group-by-time combination, supplemented by visual inspection of Q-Q plots and histograms to detect deviations from normality that may not reach statistical significance in small samples. Homogeneity of variance between groups will be verified using Levene's test for equality of variances when parametric between-group comparisons are planned. For instances where normality or homogeneity assumptions are violated (Shapiro-Wilk $p\leq0.05$ or Levene's $p\leq0.05$), pre-specified non-parametric alternatives will be implemented as detailed in subsequent sections. All assumption testing results will be documented in supplementary materials to demonstrate the appropriateness of selected analytical methods.

4. Primary Inferential Statistical Methods

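### SAP section 4 puts within-arm tests and unadjusted between-arm tests under one primary heading without saying which carries the conclusion, and leaves baseline adjustment exploratory

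*Combined protocol and SAP*

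**What the plan says.** The Objective is a between-arm one: to "compare the effectiveness of low load blood flow restriction training (LL-BFR) with traditional resistance training exercises (T-RT"). The SAP introduction also describes a comparison, of "an experimental training group (n=16) and a control group (n=16"), over three timepoints and five primary outcome domains. Two of these are continuous (muscle size, ROM) and three ordinal (strength, pain, effusion).

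The heading "4. Primary Inferential Statistical Methods" covers two families of tests.

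- **4.1, within group.** It begins "For evaluating changes over time within each experimental arm, distinct approaches will". Normally distributed outcomes get "repeated measures ANOVA with Greenhouse-Geisser correction for sphericity violations, followed by paired t-tests with Bonferroni-adjusted α levels". Non-normal and ordinal outcomes get Friedman tests followed by Wilcoxon signed-rank tests.
- **4.2, between groups.** At each timepoint the arms are compared by t, Welch or Mann-Whitney test, with a mean difference and 95% CI or a Hodges-Lehmann difference. ANCOVA on baseline is an optional exploratory step, for continuous outcomes only, to be used if a substantial baseline difference is seen. The SAP does not define substantial.

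No sentence ranks 4.1 against 4.2 or names a primary timepoint.

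**The concern.** Each test in 4.1 uses one arm only. After ACL reconstruction both arms are expected to recover, so a significant change within an arm shows recovery, with or without any effect of BFR. It does not answer the question in the Objective.

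Section 4.2 does answer that question, but only by comparing levels visit by visit, including baseline, where randomised arms differ only by chance. Change over time is formally tested only in 4.1, one arm at a time. A reader of the results who wants to know whether BFR-RT patients improved more is given two separate within-arm p-values and no test that puts them together. Contrasting those p-values is a known route to false claims.

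The baseline values that would sharpen the between-arm estimate are collected at 0–1 week. They enter it only if an undefined imbalance appears, and never for the three ordinal outcomes.

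**Working it through.** **The plan's own figure.** The plan states "Target Sample Size: 32 participants", justified as "Based on power analysis to detect clinically significant differences in muscle hypertrophy/strength". The split 16 + 16 = 32 agrees with the SAP. The power analysis itself cannot be reproduced, because no effect size, SD, alpha, power or dropout is given. For orientation, 16 per arm detects a standardised difference of (1.960 + 0.842) × √(2/16) = 0.99 at two-sided 5% and 80% power.

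**Inputs for the check.** n = 16 per arm and three timepoints come from the SAP. Three timepoints give three pairwise contrasts, so the Bonferroni level is 0.05/3 = 0.0167. The SAP states 0.05 only for its assumption tests; two-sided 0.05 for inference is an assumption. The standardised within-arm change dz (mean change divided by the SD of change) is not in the documents and is varied.

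**Discordance of the 4.1 tests.** Let p be the power of a paired t-test in one arm (noncentral t, n = 16). If both arms have the same true change, the chance that exactly one is significant is 2p(1 − p). For dz = 0.5 at 0.05: 2 × 0.465 × 0.535 = 0.498.

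| dz | p at 0.05 | one arm only | p at 0.0167 | one arm only |
|---|---|---|---|---|
| 0.3 | 0.203 | 32% | 0.096 | 17% |
| 0.4 (simulated) | 0.32 | 44% | 0.17 | 29% |
| 0.5 | 0.465 | 50% | 0.280 | 40% |
| 0.7 | 0.745 | 38% | 0.555 | 49% |
| 0.8 | 0.848 | 26% | 0.690 | 43% |
| 0.9 | 0.919 | 15% | 0.804 | 32% |
| 1.0 | 0.962 | 7% | 0.887 | 20% |
| 1.2 | 0.994 | 1% | 0.973 | 5% |
| 1.5 | about 1 | about 0% | 0.999 | 0.3% |

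The tests that 4.1 names behave alike. In simulation (3,000 trials per setting, normal data, linear change over three visits, assumed correlation 0.5), discordance at dz 0.3, 0.5, 0.7, 0.9, 1.2 and 2.0 was 25%, 47%, 46%, 24%, 2% and 0% for the Greenhouse-Geisser omnibus test. For Friedman it was 25%, 44%, 49%, 37%, 9% and 0%.

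**The direct comparison.** In the same simulations the between-arm t-test at the final visit rejected in 4.7–5.1% of trials and the t-test on change in 4.5–5.4%. A direct test therefore holds its level whatever the size of the shared recovery.

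**What baseline adjustment adds.** With baseline-to-final correlation ρ, ANCOVA multiplies the variance of the final-visit difference by about 1 − ρ². At the assumed ρ = 0.5 this is 1 − 0.25 = 0.75, and the detectable difference falls from 0.99 to 0.99 × √0.75 = 0.86. The gain vanishes as ρ approaches 0 and grows as ρ approaches 1. The documents give no ρ.

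**Volume of tests.** Section 4.1 can yield up to 5 outcomes × 2 arms × (1 omnibus + 3 post-hoc) = 40 tests. Section 4.2 yields 5 × 3 = 15, of which 5 are at baseline.

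**The case against.** The strongest reply is that section 4.2 already does what the Objective asks. It stands under the same primary heading, pre-specifies direct tests and gives effect estimates. In a randomised trial its final-visit difference is a valid estimate of the treatment effect, without any baseline adjustment. This stands.

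It also rules out a reading that the layout invites: that the plan ranks within-arm tests as its primary inference, or lacks a between-arm test. Order of listing is not a hierarchy, and the SAP introduction points to a between-arm purpose.

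A second reply is that nothing in the documents says superiority will be inferred from one arm being significant and the other not. That is also true. Such a reading is left open, but it is not planned.

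A third is that discordance is high only for moderate changes. Recovery measured from 0–1 week after surgery may well be large. Both arms would then be significant, and the 4.1 tests would be uninformative about BFR rather than misleading. This stands too; without an expected change or SD, the documents do not support saying that the arms will often look different.

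These replies do not supply a rule for which family decides, a between-arm comparison of change, or a planned use of baseline for all five outcomes.

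**Conclusion.** The point holds as a weakness in the choice and ranking of analyses. Section 4 does not say which family carries the conclusion. Its within-arm tests do not address the between-arm objective. Its valid between-arm test leaves the baseline data unused unless an undefined imbalance is observed, and then only for two of the five outcomes.

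The size of the risk from contrasting within-arm p-values is conditional: about 25–50% at a standardised change of 0.4–0.8, about 7% at 1.0 and near 0% at 1.5 or more, at alpha 0.05. The Bonferroni level shifts this range towards larger changes (20% at 1.0, 5% at 1.2). These figures assume equal true change in the arms, normal data and two-sided testing. They describe a misreading that the plan permits, not the error rate of the 4.2 tests, which is about 5% per outcome and timepoint.

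The change should be made, but the trial's comparison is not invalid without it.

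**What to change.** - For each outcome, make the baseline-adjusted between-arm difference at the post-intervention visit (8–9 weeks) the primary inference, unconditionally and not triggered by observed imbalance.
- For muscle size and ROM, use ANCOVA, or an arm-by-visit contrast from a mixed model that adjusts for baseline.
- For strength, pain and effusion, use a rank-based ANCOVA or a proportional-odds model with baseline as covariate. Choose one in advance; with 32 participants, sparse categories may make the proportional-odds model unstable.
- Make 4.1 descriptive: within-arm mean change with 95% CI, or median change, without tests.
- State that no conclusion about BFR-RT against T-RT rests on within-arm significance.

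This uses data already scheduled and reduces the number of tests. The cost is that within-arm p-values are no longer headline results. The protocol's Enrollment item lists the sample as actual, and Safety Monitoring already reports that no adverse events occurred, so data may exist. The change must therefore be dated, and labelled post hoc if outcome data have been seen. The rule on interpretation is worth adding even then.

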4.2 Between-Group Comparative Analyses

Experimental versus control group comparisons at each timepoint will employ independent samples t-tests for normally distributed continuous variables with equal variances, Welch's t-tests for unequal variances (as determined by Levene's test), and Mann-Whitney U tests for non-normal continuous or ordinal data. Between-group effect sizes will be reported as mean differences with 95% confidence intervals for parametric tests and Hodges-Lehmann median differences for non-parametric analyses. To account for baseline imbalances in this pilot study, exploratory analyses of covariance (ANCOVA) may be conducted for continuous outcomes using baseline measurements as covariates if substantial pre-intervention group differences are detected despite randomization.

5. Missing Data Handling Protocol

Missing data patterns will be formally evaluated using Little's MCAR test prior to primary analyses. Given the pilot nature of this study with limited sample size, primary analyses will employ complete case approaches with explicit reporting of missing data proportions by group and timepoint. Sensitivity analyses will compare complete case results with multiple imputation approaches using chained equations (MICE)

incorporating baseline characteristics and observed follow-up data as predictors. Participants with missing baseline data will be excluded from all analyses, while those missing later timepoints will be retained for analyses where their available data permits. A participant flow diagram will document attrition at each study phase.

6. Software Implementation and Reproducibility

All analyses will be conducted using Stata MP 18.0. Graphical outputs will adhere to STROND guidelines for transparent reporting of non-normal data distributions.

Reference:

Ardern, C. L., Webster, K. E., Taylor, N. F., & Feller, J. A. (2011). Return to sport following anterior cruciate ligament reconstruction surgery: A systematic review and meta-analysis of the state of play. *British Journal of Sports Medicine*, 45(7), 596–606. <https://doi.org/10.1136/bjsm.2010.076364>

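### SAP 4.2 compares the arms at every visit and names none as primary, so each outcome has two unadjusted post-baseline chances of a primary result

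*Combined protocol and SAP*

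**What the plan says.** The SAP introduction describes comparisons "across three key timepoints: immediate post-surgical baseline (0-1 week), mid-intervention (4-5 weeks), and post-intervention (8-9 weeks". It adds: "The study employs a repeated measures design to evaluate five primary outcome domains". The protocol, under Outcome Assessments in section 8, gives the same schedule with a different final window: "Time Points: Baseline (Week 0-1), Mid-Intervention (Week 4-5), Post-Intervention (Week 9". No visit is attached to the primary measures there, nor in the later Outcome Measures list, which begins "Muscle strength (measured using manual muscle technique). Muscle size (measured via measuring tape), ROM (Using goniometer), pain (using a Visual Analog Scale".

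The between-arm analysis is in 4.2, under the heading "4. Primary Inferential Statistical Methods". It reads "Experimental versus control group comparisons at each timepoint will employ independent samples t-tests", with Welch and Mann-Whitney tests as alternatives. Baseline is one of the listed timepoints and is not exempted. The same section gives baseline differences one use: if they are substantial, an exploratory ANCOVA may follow for continuous outcomes.

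On multiplicity, the SAP introduction says that adjustments are included. Section 4.1 provides them for post-hoc comparisons between visits within an arm. Section 4.2 contains none.

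**The concern.** An endpoint needs a measure and a time, and here the time is left open. The planned course is 16 sessions over 8 weeks, so the 4-5 week visit sees only part of it and the post-intervention visit sees the whole. The two visits answer different questions, yet both are tested under the heading for primary methods and nothing ranks them.

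Two consequences follow for any one outcome. The visit that supports the conclusion can be chosen after the results are known. And if the arms differ at one follow-up visit but not the other, the plan does not say what the trial found. The repeated measures ANOVA in 4.1 does not settle this, because it is run within each arm and gives no single between-arm answer.

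**Working it through.** **Figure to reproduce.** The plan states no error rate. Its only design figure is 32 participants (16 per arm), said to rest on a power analysis. No effect size, SD, power, alpha or visit is given, so that figure cannot be reproduced, and it does not identify a primary visit.

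**Step 1: does any section rank the visits?**
- SAP introduction: three visits, all described as key.
- Protocol section 8, Outcome Assessments: three visits, no order of importance.
- Protocol, Outcome Measures: five measures, no visit.
- Protocol section 7, Enrollment: a power analysis on hypertrophy/strength, no visit.
- SAP 4.2: tests at each timepoint.

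No section names a primary visit.

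**Step 2: how much of the course does the mid visit cover?** 16 sessions / 8 weeks = 2 per week. If weeks are counted from the start of training, weeks 4-5 correspond to 8 to 10 sessions, which is 8/16 = 50% to 10/16 = 62.5%.

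**Step 3: false-positive rate for one outcome, two follow-up visits.** Assumptions:
- Two-sided 5% for each test. The SAP gives no alpha for arm comparisons; the level is taken from "Between-group effect sizes will be reported as mean differences with 95% confidence intervals for parametric tests".
- No adjustment across visits, as 4.2 is written.
- Correlation r between the two test statistics of 0.5, 0.7 or 0.8. The documents give no value. For unadjusted comparisons on the same participants, r is the between-visit correlation of the outcome.

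Formula: P(either) = 1 − P(|Z1| ≤ 1.96 and |Z2| ≤ 1.96), with Z1 and Z2 bivariate normal with correlation r.
- r = 0 (upper reference): 1 − 0.95² = 0.0975
- r = 0.5: 0.091
- r = 0.7: 0.083 (0.0835 before rounding; a simulation of 2 million draws gave 0.084)
- r = 0.8: 0.078

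Simulating 20,000 trials with 16 per arm and ordinary t-tests gives 0.091 at r = 0.5, 0.081 at 0.7 and 0.072 at 0.9. The small sample does not change the picture.

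**Step 4: how often would the visits disagree under the null?** P(both) = 0.05 + 0.05 − P(either).
- r = 0.5: 0.100 − 0.091 = 0.009, so one visit alone is significant in (0.091 − 0.009)/0.091, about 90% of false positives.
- r = 0.8: 0.100 − 0.078 = 0.022, so (0.078 − 0.022)/0.078, about 72%.

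A chance finding would therefore usually appear at one visit only, which is the case the plan leaves undecided.

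**Step 5: effect of naming one visit.** The rate for one outcome returns to 0.05. With five outcomes, the post-baseline tests fall from 10 to 5. If all were independent, the rate would fall from 1 − 0.95¹⁰ = 0.401 to 1 − 0.95⁵ = 0.226.

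**The case against.** The best defence is that the post-intervention visit is the natural endpoint. The other follow-up visit is labelled mid-intervention, the BFR course is fixed at 8 weeks, and this is a pilot with limited numbers, in which 8-9% instead of 5% is modest. The equal standing of the visits is indeed an inference from unranked labels and a heading, and the documents state no rule for declaring success. That softens the point without removing it. The stated objective is to compare effectiveness, the sample size is attributed to power, and these tests are called primary. If the last visit was meant, the text does not say so.

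Three stronger readings are tempting, and the documents do not support them.
- **Counting all three visits as chances of success.** This would give about 12.5%, 10.9% and 9.8% at correlations of 0.5, 0.7 and 0.8. A baseline difference cannot be a treatment effect, and nothing in the plan would count it as one.
- **Treating a chance baseline difference as a primary result.** Section 4.2 uses baseline differences only as imbalance that may prompt an exploratory ANCOVA. The fair criticism is narrower: after randomisation, a significance test at baseline tells the reader nothing about treatment and should not decide the analysis.
- **Saying that the plan ignores multiplicity.** It promises adjustment in general and specifies it within arms. The gap is that the promise is not carried into 4.2.

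**Conclusion.** The point holds as a gap in the definition of the primary comparison. No visit is primary, and 4.2 as written allows two unadjusted post-baseline tests per outcome. The size for one outcome is a false-positive rate of about 9.1% to 7.8% instead of 5%, under an assumed two-sided 5% level and assumed correlations of 0.5 to 0.8. The undefined answer when the visits disagree depends on none of these assumptions.

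The change should be made, but the point is moderate in weight. A reader might infer that it accounts for the whole error rate of the trial. It does not: five primary outcomes add multiplicity that naming a visit leaves in place.

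**What to change.** - In the SAP introduction and 4.2, name the post-intervention visit as the time point of the primary between-arm comparison for each primary outcome.
- Reconcile the window of that visit, which is Week 9 in the protocol and 8-9 weeks in the SAP.
- Call the 4-5 week comparison secondary and supportive.
- Replace the between-arm test at baseline with descriptive values by arm, which SAP section 1 already plans. Do not let a baseline test trigger the ANCOVA; state in advance whether baseline will be adjusted for.
- Date the change and say whether outcome data had been seen. The protocol records enrolment as actual and says that no adverse events were reported, which suggests that the trial was well advanced. If results were known, the choice of visit is post hoc and should be reported as such.

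The cost is a short text change and no new data. The real price is that a difference seen only at 4-5 weeks can no longer be claimed as primary. Keeping both visits primary with a Bonferroni split (0.025 each) would cost more. With 16 per arm and 80% power, the detectable standardised difference is (1.960 + 0.842) × √(2/16) = 0.99 at 0.05, and (2.241 + 0.842) × √(2/16) = 1.09 at 0.025.

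### SAP 4.2 plans no confidence interval for the between-arm effect on strength, pain and effusion, and the Hodges-Lehmann estimate it names is often exactly 0 on the short scales when the arms differ modestly

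*Combined protocol and SAP*

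**What the plan says.** The SAP's opening paragraph says the study will "evaluate five primary outcome domains". Three of the five are "muscle strength (ordinal, 0-5 scale), pain perception (ordinal, VAS 0-10), and joint effusion (ordinal, 0-3 clinical scale". SAP section 2 commits these three to rank-based methods; for effusion the wording is "clinician-rated effusion scales (0=none, 3=severe) will be analyzed using non-parametric methods".

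Section 4.2 sets the between-arm test as "Mann-Whitney U tests for non-normal continuous or ordinal data". It then fixes the effect measures in one sentence: "mean differences with 95% confidence intervals for parametric tests and Hodges-Lehmann median differences for non-parametric analyses". The interval belongs to the parametric half only; the other half names just "Hodges-Lehmann median differences for non-parametric analyses".

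Three other provisions come close but do not supply a between-arm effect with its uncertainty:

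- Section 4.1 plans "rank-biserial correlations for non-parametric tests", but for change over time within an arm.
- The ANCOVA in section 4.2 is exploratory and limited to continuous outcomes.
- Section 1 plans medians, IQRs and frequency tables per grade by group and timepoint, which are descriptive.

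The documents are not uniform on outcome status. The protocol's Outcome Measures list and the SAP treat all three as primary, while the protocol's Outcome Assessments list places pain and effusion among the secondary measures. The gap is the same under either label.

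**The concern.** There are two separate problems.

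**No interval.** In a pilot with 16 patients per arm, the range of effects compatible with the data is the most useful result. Without it, a reader who sees a difference of 0 with p above 0.05 cannot tell the absence of an effect from an imprecise estimate.

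**A coarse estimator.** The Hodges-Lehmann difference is the median of all treated-minus-control pairs and is meant for a location shift. On a scale with four or six grades the pairs are whole numbers with many ties. The estimate therefore stays at 0 until more than half the pairs favour one arm, and then jumps by about a grade. A modest shift can be reported as no difference, and a significant Mann-Whitney test can stand beside an estimated difference of 0.

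**Working it through.** **Inputs from the documents.** 16 patients per arm; scales 0-5, 0-10 and 0-3; Mann-Whitney U between arms; Hodges-Lehmann difference without an interval. The plan states no figure for this estimate and no score distributions, so there is nothing of its own to reproduce. All distributions below are assumptions.

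**Worked example (invented strength data, 16 per arm).** Control: 8 at grade 3 and 8 at grade 4. Treated: 2 at grade 3 and 14 at grade 4.

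1. Pairs: 16 × 16 = 256. Difference +1: 14 × 8 = 112. Difference -1: 2 × 8 = 16. Ties: 256 - 112 - 16 = 128.
2. Hodges-Lehmann is the median of the 256 differences. Ordered, there are 16 of -1, then 128 of 0 (positions 17 to 144), then 112 of +1. Positions 128 and 129 are both 0, so the estimate is **0**.
3. Mann-Whitney: U = 112 + 128/2 = 176, with mean 128 under the null. Tie groups are 10 and 22, so Σ(t³ - t) = 990 + 10,626 = 11,616. Variance = (256/12) × [33 - 11,616/(32 × 31)] = 21.33 × 21.29 = 454.2, and SD = 21.31. Then z = 48/21.31 = 2.25 and **p = 0.024** (0.026 with continuity correction).
4. Probability of superiority: P = 176/256 = **0.69**. Between-group rank-biserial: 2P - 1 = 0.375.
5. 95% interval for P from the placement values:
   - Treated: 0.75 (14 patients) and 0.25 (2 patients), variance 0.4375/15 = 0.0292.
   - Control: 0.9375 (8 patients) and 0.4375 (8 patients), variance 1/15 = 0.0667.
   - SE = √[(0.0292 + 0.0667)/16] = 0.077.
   - Interval: 0.6875 ± 1.96 × 0.077 = **0.54 to 0.84**.
6. The 95% interval for the Hodges-Lehmann difference would be 0 to 1.

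As written, section 4.2 would report a difference of 0 with p = 0.024 and no interval.

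**Counter-example (effusion grades 0/1/2/3).** Control 3/6/5/2, treated 8/6/2/0: Hodges-Lehmann = -1 (95% interval -1 to 0), p = 0.023. The estimate is not always 0.

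**How often it is exactly 0.** Simulation with 16 per arm, 2,000 trials per scenario and a proportional-odds shift. The ranges cover four assumed control distributions on 0-3 and three on 0-5.

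| Scale | OR 1.5-2 | OR 3 | OR 4 | OR 6 | OR 10 |
|---|---|---|---|---|---|
| 0-3 | 55-90% | 38-81% | 26-73% | 13-66% | 4-58% |
| 0-5 | 61-90% | 38-62% | 25-49% | 10-31% | 2-17% |

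A separate run of 4,000 trials per scenario at OR 3 agrees:

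| Assumed control shares | Estimate = 0 | Estimate = 0 among significant results |
|---|---|---|
| Strength grades 2-5: 5/30/45/20% | 51% | 1% |
| Strength grades 2-5: 2/18/55/25% | 64% | 8% |
| Effusion grades 0-3: 35/40/20/5% | 58% | 6% |
| Effusion grades 0-3: 50/35/12/3% | 80% | 39% |

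Across the wider set at OR 3 or more, the last column is 0-11% on 0-5 and 0-5% on 0-3, but 40-45% where half the controls score 0 on effusion.

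**Whether this is only sampling noise.** Take control strength of 2/18/50/30% in grades 2-5 and OR 3. In the population, the treated patient scores higher in 47% of pairs, ties in 36% and scores lower in 17%. Since 47% is below half, the population Hodges-Lehmann value is itself 0, while the probability of superiority is 0.47 + 0.36/2 = 0.65. At OR 4 the first share reaches 51% and the population value becomes 1.

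**Pain, 0-10.** With a 1-point shift and an assumed SD of 1.5 to 2.5, the estimate is 0 in 17-25% of trials, and never among the significant results simulated.

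**The case against.** A reader might infer that the estimate is usually 0 whenever the arms differ. The documents give no score distributions that would support this, and the calculations contradict it for large effects. At OR 10 the share is 2-17% on the 0-5 scale, and on 0-3 it is as low as 4%. For the larger differences that 16 per arm could detect, the estimate is usually one grade in either direction. Only floor-heavy effusion keeps the share high.

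Other points for the plan:

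- *Low power explains much of it.* Mann-Whitney power at OR 3 is about 30-37%, so many modest shifts would be missed whatever the summary. This stands in part. But the population value can itself be 0 at OR 3, which is a property of the estimator, and low power makes an interval more necessary.
- *The frequency tables would show a masked shift.* They would, and counts per grade need not be added. They carry no estimate of the arm difference and no uncertainty.
- *The interval is implied.* The sentence states it for one method and omits it for the other. An implied interval would also leave the coarseness.
- *Rank-biserial is already planned.* Only within arms, alongside the signed-rank test. That paired version usually drops zero changes and is not the between-group measure proposed here.
- *A significant test beside a 0 is rare.* That is so in most assumed cases; the figure near 40% rests on one assumed type of effusion distribution.

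**Conclusion.** The concern holds in limited form. On the text, it is clear that no interval is specified for the between-arm effect on strength, pain or effusion, and that no other between-arm effect measure is named for them. The coarseness is real on the 0-3 and 0-5 scales for modest differences: about 40-80% exact zeros at an odds ratio of 3, and fewer at larger effects outside floor-heavy effusion. It is milder for pain. All percentages depend on assumed score distributions and a proportional-odds shift (for pain, an assumed mean shift and SD), and should be read as ranges.

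Nothing here shows that the Mann-Whitney test is invalid or that any p-value would change. This is a gap in estimation and reporting, cheap to close and worth closing before the results are written up.

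**What to change.** In SAP section 4.2, state that for strength, pain and effusion the between-arm effect at each timepoint will be the Mann-Whitney probability that a BFR-RT patient has the better score than a T-RT patient, ties counted half, with a 95% confidence interval. The between-group rank-biserial correlation, 2P - 1, is equivalent. Give a 95% interval for any Hodges-Lehmann difference that is kept, for example for pain. Present these beside the frequency tables already planned in section 1.

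A baseline-adjusted proportional-odds ratio is possible, but it swaps one assumption for another and may be unstable with 32 patients and sparse grades, so it is not needed to close the gap.

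The cost is about one sentence, with no new data and no change of test. The downside is that clinicians know a difference in grades better than a probability, so a short explanation should go with the result.
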